# **6.4.2.1.** Sensitivity Analyses

The following sensitivity analyses will be performed on the key efficacy endpoints as follows:

- Primary efficacy endpoint (ORR) based on the Per-protocol Analysis Set using a similar analysis method as the primary analysis
- ORR and PFS based on assessments by the investigator or local radiologist on the Efficacy Population

# 6.4.3. Subgroup Analyses

To assess consistency of treatment effects in different subsets, IRC assessed ORR (primary analysis) will be summarized for the following subgroups.

- Age group (<65,>=65)
- Gender (male, female)
- Race (Caucasian/white, Black, Asian, Other)
- Baseline ECOG score (0, 1)
- Prior systemic therapy 1 line, 2 lines, and 3 or more lines for advanced/metastatic disease
- North America, Europe, Asia Pacific (excluding Japan), Japan,
- Prior surgical resection of primary tumor (Yes, No)
- Prior (neo) adjuvant treatment (Yes, No)
- Baseline *FGFR* rearrangements status by local lab (commercial test provided to clinician as standard of care based on tumor tissue) and/or central lab (clinical trial assay performed on tumor tissue)
- Patients with solid tissue sample and report

# 6.5. Safety Analyses

All safety analyses will be performed considering all treated patients.

#### 6.5.1. Extent of Exposure

# 6.5.1.1. Administration of Study Drug

The number of cycles initiated and completed, extent of exposure (Treatment Duration) relative dose intensity in all cycle and total dosage for TAS-120 will be summarized.

Relative dose intensity (RDI) is defined as the ratio of the amount of drug actually administered to the amount planned in the study for TAS-120. The relative dose intensity is calculated in the following steps:

- 1. Amount of drug actually administered is total number of dose administered
- 2. Treatment Duration = last dose date first dose date +1
- 3. Amount of drug planned for the patient =Treatment Duration
- 4. Relative Dose Intensity = (Amount of drug actually administered / Amount of drug planned) x 100%

A by-patient listing of dosing of study medication will be also provided.

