8. STUDY DRUG

8.1. Study Drug Administration and Dose Modification Procedures

8.1.1. Study Drug Administration

TAS-120 is supplied as 4 mg tablets. The dose for TAS-120 is 20 mg QD. Patients should follow the instructions of the treating physician on study drug administration during treatment. Patients are required to fast for at least 2 hours before and 1 hour after administration of TAS-120. Patients will be permitted to drink water during this period. Dietary restrictions that limit phosphate intake may reduce the risk of hyperphosphatemia (see [Section 7.8](#)). On non-PK sampling days, TAS-120 can be administered in the morning or evening at the same time (if possible) each day. If a patient misses a dose (i.e., did not take TAS-120 for > 12 hours of the scheduled time of that day), the patient should take the dose on the next day.

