8.2.4. Patient Instructions for Handling Study Drug

The patient must be instructed in the handling of TAS-120 as follows:

- To only remove the amount of TAS-120 needed at the time of dosing.
- Not to remove doses in advance of the next scheduled dosing.
- To bring all used and unused blister packs to the site at each visit.
- TAS-120 should be kept in a safe place and out of sight and reach of children.
- TAS-120 should be taken with a glass of water on an empty stomach (2 hours after and 1 hour before a meal).
- Doses are not to be replaced if the patient misses a dose or vomits a dose and administration of study drug should follow the direction of the treating physician.
- Patients should make every effort to take doses on schedule.
- To report any missed doses.

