### **5.2.** Treatment Groups

There are 8 disease groups in this Phase I Expansion study as described in section 4.1 of this SAP. 20 mg QD of TAS-120 has been selected as the dose for each of the 8 disease groups.

In addition, in early portion of the Phase I Expansion study, a small number of patients were treated with 16 mg DQ and then followed by 20 mg QD.

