Time to event distribution (e.g. progression free survival, overall survival, time to response, and duration of response) will be estimated using Kaplan Meier techniques. When appropriate, the median along with the corresponding log-log transformed 95% CI will be estimated. Rates at fixed time points will be derived from the Kaplan Meier estimate and corresponding confidence interval will be derived based on Greenwood formula for variance derivation and on log-log transformation applied on the survivor function S(t). Confidence intervals for binomial proportions, ORR and DCR, will be derived using the Clopper-Pearson method.

For patients who were also treated with 16 mg QD during early portion of the Phase I Expansion of the study, separate analysis will be presented.

All the analyses of efficacy, safety, and PK data for this study will be performed using SAS® statistical software package, Version 9.3 or a later version.

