#### 6.5.1.2. Modification of Study Drug

The number and percentage of patients with at least one dose interruption along with reason for the interruptions will be summarized by cohort.

The number and percentage of subjects with at least one dose reduction and reason for the dose reduction will be summarized.

By-patient listings of dose interruptions and dose reductions will be also provided.

In addition, summary tables will also be provided for the iCCA patients by the categories of: with FGFR2 rearrangement, without FGFR2 rearrangement, with FGFR2 rearrangement with GEM/CIS and without FGFRi Prior Treatment, with FGFR2 rearrangement with FGFRi prior treatment.

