#### 6.5.1.2. Modification of Study Drug

The number and percentage of patients with at least one dose interruption along with reason for the interruptions will be summarized.

The number and percentage of patient with at least one dose reduction and reason for the dose reduction will be summarized. Time to first dose reduction and interruption will be summarized.

By-patient listings of dose interruptions and dose reductions will be also provided.

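### Phase 2 and Expansion relative dose intensity counts doses, not milligrams, so dose reductions never lower it; the Escalation QOD formula does not fit Monday/Wednesday/Friday dosing

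*SAP*

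**What the plan says.** **Phase 2 and Expansion.** Section 6.5.1.1 of each SAP introduces RDI as a ratio of drug amounts, given over planned, and then derives it in the same four steps. The numerator step reads "Amount of drug actually administered is total number of dose administered". Treatment duration is last dose date minus first dose date plus 1. The denominator step reads "Amount of drug planned for the patient =Treatment Duration". RDI is the ratio times 100.

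**Dose levels and missed doses.** The protocol dose is 20 mg QD (Section 8.1.1), with two permitted reductions, to 16 mg and to 12 mg (Section 8.1.3.1, Table 5). After a missed dose "the patient should take the dose on the next day" (Section 8.1.1), and "Doses are not to be replaced if the patient misses a dose or vomits a dose" (Section 8.2.4). A missed dose is therefore lost from the count.

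**Related reporting.** Both SAPs also summarize total dosage and list dosing by patient (6.5.1.1). The Expansion SAP reports "The number and percentage of subjects with at least one dose reduction", with reasons (6.5.1.2). The Phase 2 SAP does the same and adds: "Time to first dose reduction and interruption will be summarized" (6.5.1.2). The Expansion SAP notes that early on "a small number of patients were treated with 16 mg DQ and then followed by 20 mg QD" (5.2). For those treated at 16 mg "during early portion of the Phase I Expansion of the study, separate analysis will be presented" (6.1).

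**Dose Escalation.** Section 10.1 of that SAP uses mg throughout. Planned weekly dose is the dose level times 7 for QD and times 3.5 for QOD. Duration is last minus first dose date, plus 1 for QD and plus 2 for QOD. The same SAP's glossary and Section 4.5, and Table 3 of the protocol, define QOD as Monday, Wednesday and Friday. The footnote to protocol Table 4 (Section 5.2.2) expands QOD as every other day.

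**The concern.** The Phase 2 and Expansion derivation does not produce the quantity it defines. Doses over days is the share of treatment days on which a dose was taken, which is a compliance measure. Reading the numerator as mg does not help, because the denominator would still be days.

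The gap matters because a reduction can happen without any break in dosing. Table 7 of the protocol, offered as suggested guidance, reduces the dose first for Grade 3 hyperphosphatemia and interrupts only if two reductions fail. Footnote a of Table 6 also leaves reduction or interruption to the investigator in some circumstances. Where a hold does come first, the formula registers the hold but not the lower dose that follows. A reader who takes the SAP's definition at face value would read an RDI near 100% as near-full dose.

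The Escalation problem is separate. The 3.5 factor and the plus-2 rule suit alternate-day dosing. Under a three-a-week schedule, the formula marks down fully compliant QOD patients but not QD patients, and RDI is tabulated by schedule.

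**Working it through.** **Inputs.** Planned dose 20 mg (protocol 8.1.1); reduced levels 16 and 12 mg (Table 5); RDI steps from Section 6.5.1.1 of the Phase 2 and Expansion SAPs; QOD factor 3.5 and the plus-2 rule from Section 10.1 of the Escalation SAP.

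**Formulas compared, Phase 2 and Expansion**
- As written: number of doses / treatment days × 100.
- By mg: total mg taken / (20 × treatment days) × 100.

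*Limits with a dose every day.* As written, the result is 100% at 20, 16 or 12 mg. By mg, the limits are 20/20 = 100%, 16/20 = 80% and 12/20 = 60%. For a patient starting at 20 mg, 60% is approached but not reached.

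*Mixed reading.* A compliant 20 mg patient with mg over days would score 20/1 × 100 = 2000%, so the text works only as a count.

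*Illustrations.* All assume reductions on Days 8 and 22 and no re-escalation. Doses are 7 at 20 mg, 14 at 16 mg, and the rest at 12 mg. The first two rows assume hyperphosphatemia resolves to Grade 2 or lower within 14 days of the second reduction, so that Table 7 calls for no interruption. The third row follows the same path with 10 missed doses. In the last two it does not resolve, and a hold is assumed.

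| Course | As written | By mg |
|---|---|---|
| 12 weeks, none held or missed | 84/84 = 100% | (140 + 224 + 12×63)/1680 = 66.7% |
| 24 weeks, none held or missed | 168/168 = 100% | (140 + 224 + 12×147)/3360 = 63.3% |
| 12 weeks, 10 doses missed at 12 mg | 74/84 = 88.1% | (140 + 224 + 12×53)/1680 = 59.5% |
| 12 weeks, hold on Days 36–49 | 70/84 = 83.3% | (140 + 224 + 12×49)/1680 = 56.7% |
| 24 weeks, same hold | 154/168 = 91.7% | (140 + 224 + 12×133)/3360 = 58.3% |

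*Milder course.* One reduction to 16 mg on Day 22 of 126 days gives 100% as written and (20×21 + 16×105)/(20×126) = 83.3% by mg.

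*Hold only.* Fourteen days held out of 126 at 20 mg gives 112/126 = 88.9% either way. The formula sees interruptions and misses reductions.

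**Escalation QOD.** Every other day is 7/2 = 3.5 doses a week, which reproduces the SAP's factor. Monday/Wednesday/Friday is 3. Step 3 labels the duration as weeks but writes a difference in days, so I divide by 7 to honour the stated unit. With full compliance:
- Every other day, 11 doses, 20 + 2 = 22 days: 11/(22/7)/3.5 = 100%.
- Monday start, 1 week: 3/(6/7)/3.5 = 100%.
- Monday start, 3 weeks: 9 doses, 18 + 2 = 20 days, 9/(20/7)/3.5 = 90.0%.
- Monday start, 12 weeks: 36/(83/7)/3.5 = 86.7%. Limit: 3/3.5 = 85.7%.
- Wednesday or Friday start, 3 weeks: 9/(21/7)/3.5 = 85.7%.
- QD, one cycle: 21/(21/7)/7 = 100%.

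Replacing 3.5 by 3 alone overshoots: Monday start, one cycle, 9/(20/7)/3 = 105%.

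**The case against.** The best defence is that little depends on RDI. It is descriptive, and the plan already reports total dosage, treatment duration, dosing listings, and counts and reasons for reductions, with time to first reduction in Phase 2. That stands and limits the size of the point. It does not make the derivation match the definition, and none of those tables expresses delivered dose relative to plan.

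The tabulated illustrations are also steep. Many reductions follow a hold: Table 6 for Grade 3 events, Table 7 for Grade 4 hyperphosphatemia, and every reduction in Table 8. The documents give no expected reduction rate, so the effect on the summarized RDI cannot be stated. That stands too. The 100/80/60% limits do not depend on the path chosen.

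On QOD, the every-other-day footnote sits under a table whose body is redacted, so the trial it describes cannot be seen. The mismatch inside the Escalation SAP, 3.5 against three a week, does not need that footnote. The percentages do need the division by 7. Taken literally in days, even a compliant QD patient would score 21/21/7 = 14.3% over one cycle, so the conversion must be intended. Escalation is complete, 20 mg QD was carried forward, and that SAP also reports an average daily dose, total dosage and reductions, so the practical effect is small.

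**Conclusion.** The concern holds. As written, Phase 2 and Expansion RDI is a dose-count compliance figure that no dose reduction can lower. With a dose every day it reads 100%, where the mg-based value lies between just above 60% and 100% for a patient starting at 20 mg. The course-specific figures rest on assumed reduction days, holds and missed doses; the bounds rest only on the protocol's dose levels.

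The Escalation QOD denominator agrees with alternate-day dosing and not with Monday/Wednesday/Friday. Under the latter, full compliance scores 90.0% over one cycle for a Monday start and tends to 85.7%, given the days-to-weeks conversion.

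The effect is minor to moderate for Phase 2 and Expansion and smaller for Escalation. No efficacy, sample-size or error-rate figure changes. The SAPs should still be corrected, because the reported number would not be what its definition says.

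**What to change.** **Phase 2 and Expansion SAPs, 6.5.1.1.** Define RDI = total mg taken / (assigned starting daily mg × treatment duration in days) × 100. The assigned dose is 20 mg, or 16 mg for the period so assigned in the early Expansion patients, who are already analysed separately. Keep doses over days as a second measure, labelled compliance.

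**Escalation SAP, 10.1.** First reconcile the protocol Table 4 footnote with protocol Table 3 and with the SAP's glossary and Section 4.5. Then define QOD RDI = total mg taken / (dose level × number of doses scheduled from first to last dose under the reconciled definition) × 100. If that definition is Monday/Wednesday/Friday, a compliant cycle gives 9/9 = 100%. This replaces the 3.5 factor and the plus-2 rule together.

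**Cost.** SAP wording and one derived variable per SAP. The dosing data are already planned for reporting, so nothing new is collected. Reported Phase 2 and Expansion RDI will be lower wherever doses were reduced.

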#### 6.5.1.2. Modification of Study Drug

The number and percentage of patients with at least one dose interruption along with reason for the interruptions will be summarized.

The number and percentage of patient with at least one dose reduction and reason for the dose reduction will be summarized. Time to first dose reduction and interruption will be summarized.

By-patient listings of dose interruptions and dose reductions will be also provided.

#### **6.5.2.** Adverse Events

#### **6.5.2.1.** Deaths

All deaths including death due to disease progression occurring in screening, on treatment, 30-day safety follow-up, or survival follow-up periods will be summarized. The reasons of death will also be summarized. The reasons are categorized in the following terms:

- Radiological Disease Progression
- Clinical Disease Progression
- Toxicity
- Adverse Event
- Other

A by-patient listing of all deaths will be provided for the All Treated Patient population.

#### 6.5.2.2. Serious Adverse Events

A serious Adverse Event (SAE) is an AE which falls into one or more of the following categories:

- Results in death
- Is life-threatening
- Requires inpatient hospitalization or prolongation of existing hospitalization
- Results in persistent or significant disability or incapacity
- Is a congenital anomaly/birth defect
- Is any other important medical event

Serious AEs will be summarized with the following categories:

- Overall summary of SAEs by worst CTC grade (grade 1, 2, 3, 4, 5, any grade, Grade 3-5) presented by SOC/PT.
- A summary of serious AEs, overall and by system organ class and preferred term.

Summary of treatment-related serious AE and by-patient listing of SAEs will also be provided.

### 6.5.2.3. Adverse Events Leading to Discontinuation of Study Drug

AEs leading to discontinuation will be summarized by treatment group:

- Overall summary of AEs leading to discontinuation by worst CTC Grade (grade 1, 2, 3, 4, 5, any grade, Grade 3-5) presented by SOC/PT
- Overall summary of treatment-related AEs leading to discontinuation by worst CTC grade (Grade 1, 2, 3, 4, 5, any grade, Grade 3-5) presented by SOC/PT

A by-patient listing of AEs leading to discontinuation will also be provided.

#### 6.5.2.4. Adverse Events Leading to Dose Modification

AEs leading to dose modification (including dose interruption or reduction) will be summarized by treatment group:

- Overall summary of AEs leading to modification by worst CTC Grade (grade 1, 2, 3, 4, 5, any grade, Grade 3-5) presented by SOC/PT
- Overall summary of treatment-related AEs leading to discontinuation by worst CTC grade (Grade 1, 2, 3, 4, 5, any grade, Grade 3-5) presented by SOC/PT

A by-patient listing of AEs leading to modification will also be provided.

#### 6.5.2.5. Adverse Events

An adverse event (AE) is any untoward medical condition that occurs in a patient while participating in this clinical study. Adverse events will be coded according to the Medical Dictionary for Regulatory Activities (MedDRA 22.0) terminology and the severity of the toxicities will be graded according to the NCI CTCAE, v4.03, where applicable.

Adverse Events that occur from the initiation of TAS-120 medication administration to 30 days after the last dose of study medication, and do not necessarily have a causal relationship to the use of the study medication will be summarized.

Number of patients with AEs will be presented by system organ class in the overall column in decreasing order. Within each system organ class, the number of patients with AEs will be displayed by preferred term (PT) in descending order.

The following adverse event summary tables will be generated:

- 1) An overall summary with the number and percentage of patients reporting AEs, serious AEs, grade 3 or higher AEs, treatment-related AEs, AEs leading to study treatment (TAS-120) discontinuation and AEs with outcome of deaths.
  - In the summary, a patient is counted once at the system organ class and once at each preferred term within the system organ class. Additional summary by system organ class, preferred term and grade (including Total and >= grade 3 categories) will also be generated.
- 2) Study-treatment-related AEs overall and by system organ class and preferred term. Additional summary by system organ class, preferred term and grade (including any grade and >= grade 3 categories) will also be generated.
  - All those AEs with relationship to TAS-120 marked as "Related" or missing will be reported in the table.
- 3) AEs by highest grade (worse severity) overall and by system organ class and preferred term.
  - In the summary, a patient is counted once at the highest grade for which the event occurred in the system organ class and the highest grade for each unique preferred term within that system organ class. Therefore, patients may only contribute once to each preferred term and once to each system organ class. The missing severity grade will be reported in a separate category.
- 4) Grade 3 or higher AEs, overall and by system organ class and preferred term
- 5) Study-treatment related AEs by grade (severity), overall and by system organ class and preferred term
- 6) AEs leading to study treatment termination, overall and by system organ class and preferred term. Additional summary by system organ class, preferred term and grade (including Total and >= grade 3 categories) will also be generated.
- 7) AEs with outcome of deaths, overall and by system organ class and preferred term

The time to onset of some special AEs of interest in the study may be summarized if appropriate.

Severity of hyperphosphatemia will be graded based on serum phosphate levels as illustrated in Table 8 using identical derivation criteria as specified in the protocol (Protocol section 8.1.3.1.1,).

In addition, hyperphosphatemia toxicities grading based on CTCAE v5.0 will also be provided using the derivation criteria presented in Table 9.

Table 8. Hyperphosphatemia Toxicity Grading based on serum phosphate levels as specified in Protocol \*

	Grade 1	Grade 2	Grade 3	Grade 4
Serum Phosphorus Result	( 0 /	$5.5 \le P \le 7.0 \text{ (mg/dL)}$	$7.0 < P \le 10.0 \text{ (mg/dL)}$	P > 10.0  (mg/dL)
( /17 1 1/7)		$1.78 \le P \le 2.26 \text{ mmol/L}$	$2.26 < P \le 3.23 \text{ (mmol/L)}$	P > 3.23 (mmol/L)

\* Section 8.1.3.1.1, protocol amendment 9

Table 9. Hyperphosphatemia Toxicity Grading per CTCAE v5.0 and derivation criteria

	Grade 1	Grade 2	Grade 3	Grade 4	Grade 5
CTCAE v5.0 criteria	Laboratory finding only and intervention no indicated	Noninvasive intervention indicated	significant but no		Death
Derivation criteria	Serum phosphat > ULN	> ULN AND concomitant	Serum phosphate > ULN AND Concomitant therapy with phosphate binder AND SAE ohyperphosphatemia/related toxicity*	Serum phosphate > ULN  AND  Concomitant therapy with phosphate binder  AND  SAE ohyperphosphatemia/ related toxicity with immediately life threatening consequences*	hyperphosphatemia or related toxicity*

\* as assessed by the sponsor

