Phosphate-lowering therapy must be started within 24 hours after observing elevated phosphorus (≥ 5.5 mg/dL [≥ 1.78 mmol/L]). Serum phosphorus is to be tested 4 days (± 24 hours) after Day 1 of Cycle 1 to initiate early intervention for hyperphosphatemia.

Hyperphosphatemia management should follow institutional practice with phosphate binding agents, such as Sevelamer, acetazolamide or Fosrenol, or other phosphate binders or a combination of these agents. Sevelamer (both tablets and powder) should preferably be taken during meals in order to improve gastrointestinal tolerance and compliance. Lanthanum carbonate (Fosrenol) should be taken immediately after meals; tablets may be cut if required for administration. Other phosphate binders and hyperphosphatemia treatment drugs may also be used. In addition, actively managing constipation by drinking water and following dietary guidelines (see [Appendix E](#)) may also decrease the risk of hyperphosphatemia.

Refer to [Section 8.1.3.1.1](#) for details on dose interruption or reduction in the management of hyperphosphatemia.

Drug interactions with TAS-120

Drug interaction studies have not been conducted in humans. The following information is based on results from *in vitro* studies. Caution is advised if these drugs are given concomitantly (see [Appendix F](#), Classification of Substrates, Inhibitors, and Inducers of CYP Enzymes and Transporters).

Cytochrome P450 (CYP) 3A inhibitors and inducers: CYP3A is involved in the metabolism of TAS-120. CYP3A inhibitors and inducers may alter the concentration and activity of TAS-120.

CYP3A substrates: TAS-120 is a potential time-dependent inhibitor of CYP3A. TAS-120 may increase the concentration and activity of CYP3A substrates.

P-glycoprotein (P-gp) and breast cancer resistance protein (BCRP) substrates and inhibitors: TAS-120 is a substrate of P-gp and BCRP, and a potential inhibitor of P-gp and BCRP. TAS-120 may alter the PK and activity of P-gp and BCRP substrates. P-gp and BCRP inhibitors may alter the concentration and activity of TAS-120.

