- Phosphate binder can be used as monotherapy or in combination. Please consult the drug package insert. Sevelamer should be preferably taken in the middle of meals, both tablets and powder, in order to improve gastrointestinal tolerance and compliance. If Sevelamer cannot be used, other Phosphate binders or hyperphosphatemia treatment drugs can be used. Lanthanum carbonate should be taken instead just after meals – tablets of Fosrenol® are quite big, but can be cut if required. No dose adjustments are needed in patients with renal or hepatic impairment.
- Titrate the dose every 2-3 weeks until an acceptable serum phosphate level is reached.

If there is any uncertainty about continuing therapy or resuming therapy in a patient with Grade ≥ 3 nonhematologic AEs, the case must be discussed with the Sponsor’s Medical Monitor prior to continuing TAS-120.

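### Phase 2 SAP Table 9 makes a phosphate binder a condition of CTCAE v5.0 Grades 3 and 4, so a serious non-fatal hyperphosphatemia case with no recorded binder can reach neither grade

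*SAP*

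**What the plan says.** Phase 2 SAP section 6.5.2.5 grades hyperphosphatemia in two ways. Table 8 uses the serum phosphate level alone. Table 9 is supplementary: "In addition, hyperphosphatemia toxicities grading based on CTCAE v5.0 will also be provided using the derivation criteria presented in Table 9".

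The derivation row of Table 9 reads as follows.

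- Grade 1: "Serum phosphat > ULN", with no further condition. The CTCAE row describes this grade as "Laboratory finding only and intervention no indicated".
- Grade 2: the legible text is "> ULN AND concomitant"; the rest of the cell is cut off.
- Grade 3: "Serum phosphate > ULN AND Concomitant therapy with phosphate binder AND SAE ohyperphosphatemia/related toxicity".
- Grade 4: phosphate above ULN, again "Concomitant therapy with phosphate binder", and an SAE with immediately life-threatening consequences.
- Grade 5: a fatal outcome; the cell is incomplete.

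The table's one footnote leaves an assessment to the sponsor. Its asterisk follows the SAE or toxicity element in Grades 3 to 5, not the binder element.

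On treatment, Protocol section 7.7 states "Phosphate-lowering therapy must be started within 24 hours after observing elevated phosphorus", with the threshold at 5.5 mg/dL. In Protocol Table 7 (section 8.1.3.1.1), between ULN and 5.5 mg/dL a binder is only to be considered. A footnote to that table adds: "If Sevelamer cannot be used, other Phosphate binders or hyperphosphatemia treatment drugs can be used".

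**The concern.** In Table 9, the SAE is what separates Grades 3 and 4 from the lower grades. Joining a treatment record to it by AND lets the absence of one class of drug cancel the seriousness of the event. A patient with a serious event would then carry a grade that the same table reserves for an isolated laboratory finding, so the table would contradict itself for that patient.

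Hyperphosphatemia is the adverse event of special interest that the SAP names in section 6.5.2.6. The SAP's revision history says the v5.0 analysis was added to make its assessment comprehensive. What is at stake is the v5.0 Grade 3 or higher rate for that event.

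**Working it through.** No sample size or error rate is involved. The check is a truth table of the derivation row.

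**Inputs.** The Grade 1, 3 and 4 derivation cells are taken as printed. The Grade 2 cell is read as phosphate above ULN plus a binder, by analogy with Grades 3 and 4, because its end is missing. A patient is given the highest grade whose conditions are all met. Grade 5 is left out because its cell is incomplete.

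**Result, given phosphate above ULN:**

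| Binder | SAE | Life-threatening | Table 9 as written | Binder condition removed from Grades 3 and 4 |
|---|---|---|---|---|
| no | no | no | 1 | 1 |
| no | yes | no | 1 | 3 |
| no | yes | yes | 1 | 4 |
| yes | no | no | 2 | 2 |
| yes | yes | no | 3 | 3 |
| yes | yes | yes | 4 | 4 |

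Only rows two and three change. Every patient on a binder keeps the same grade. If the missing part of the Grade 2 cell covers more than binders, some patients in rows two and three would be Grade 2 as written, but still not Grade 3 or 4.

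**Can rows two and three occur?** The documents leave four routes.

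1. Section 7.7 starts therapy within 24 hours after the raised value is seen. An SAE present at first detection can precede any binder, and the legible text of Table 9 sets no time window for concomitant use.
2. Section 7.7 and the Table 7 footnote allow other hyperphosphatemia drugs in place of binders.
3. Between ULN and 5.5 mg/dL, Table 7 only asks that a binder be considered, so a patient there may properly have none.
4. A binder may have been given but not recorded.

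**Size.** For one patient the understatement is 3 − 1 = 2 grades for an SAE and 4 − 1 = 3 grades for a life-threatening SAE. If the Grade 2 cell catches the case, it is 3 − 2 = 1 and 4 − 2 = 2. For the table, with about 100 treated patients, each case moves the Grade 3 or higher rate by 1/100, or 1 percentage point. The documents give no figure for how many cases to expect.

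**The case against.** The strongest case on the other side is that this will hardly ever matter. Phosphate-lowering therapy is mandatory from 5.5 mg/dL, so a serious case with no binder should be rare. Table 9 is supplementary. Table 8 still grades any value above 10 mg/dL as Grade 4, and section 6.5.2.2 still summarizes and lists every SAE. All of this stands and limits the weight of the point. It does not make the rule correct, because the rule assigns a definite and wrong grade when the case does occur.

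A reader might also infer more than the documents support:

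- **That the CTCAE row has no binder condition for Grades 3 and 4.** Those cells are cut off or empty in the available text, so this cannot be checked. The point does not need it: the derivation cells and the Grade 1 description are enough.
- **That Grade 2 has the same fault.** Its derivation cell is truncated, so no fault is established.
- **That interrupting TAS-120 is offered in place of a binder.** For protocol Grade 4, Table 7 pairs interruption with intensified phosphate-lowering therapy.
- **That acetazolamide is a treatment outside the binder condition.** Section 7.7 and Table 7 both list it among the binders. Only the residual group of other drugs remains.
- **That disagreement with Table 8 is itself an error.** The two scales rest on different bases and are meant to differ. Table 9 can also give the higher grade: at 5.0 mg/dL (assuming ULN is below that), a patient on a binder with a related SAE is Grade 1 in Table 8 and Grade 3 in Table 9. The downward-only effect applies to the no-binder cases, not to Table 9 against Table 8 in general.

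**Conclusion.** The point holds for serious or life-threatening non-fatal cases with phosphate above ULN and no recorded binder. As written, Table 9 cannot place them in Grade 3 or 4; on the legible text they are Grade 1, or at most Grade 2. For these cases any error in the v5.0 Grade 3 or higher rate is an understatement, of about 1 percentage point per case in 100 patients. The number of cases is unknown and probably small.

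This rests on two assumptions: that the highest grade with all conditions met is assigned, and that no override stands in the lost parts of the table. The effect is confined to the supplementary v5.0 table. The protocol-level grading, the SAE summaries and the efficacy analyses are untouched. The correction is still worth making, because this is a stated rule that yields a wrong grade and it costs almost nothing to repair.

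**What to change.** In SAP Table 9, remove the binder condition from the Grade 3 and Grade 4 derivations. Keep phosphate above ULN and the SAE, with Grade 4 if the SAE is immediately life-threatening. Alternatively, keep the cells and add a sentence that the SAE criterion takes precedence over binder status. Leave the Grade 2 derivation as it is: a phosphate cut-off there would be a preference and is not needed for this point. Phosphate above ULN should also stay, since nothing is wrong with it.

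The cost is one SAP edit and one derivation program. No grade changes for a patient on a binder, and no clinical rule is involved. The reported v5.0 Grade 3 or higher rate may rise slightly.
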